3.1 Background

Vitiligo is an acquired, non-contagious skin disorder characterised by depigmented patches of skin that may appear in a localised or very generalised distribution, and affecting 0.5-2.0% of the global population.(1) The exact cause of the loss of functioning melanocytes in vitiligo remains unknown, but is likely to be resulted from the complex interplay of genetics, oxidative stress, and autoimmunity.(2)

Although vitiligo is typically asymptomatic, recent Pfizer-funded research has demonstrated the condition substantially affects psychological wellbeing.(3) This previous study showed that people with vitiligo have a considerable excess mental health burden when compared with people without vitiligo. It also showed that, in people with vitiligo, mental health comorbidity is associated with higher levels of healthcare utilisation, time off work, and unemployment.(3) This increased burden could be due to the unpredictable prognosis, the current lack of cure, the perception and emotional burden associated with the visibility of vitiligo, or a combination of these factors.

There is substantial scope to extend the initial analysis, with a comprehensive assessment of sociodemographic disparities in healthcare utilisation and in the burden of mental health comorbidity in people with vitiligo. Whilst the previous Pfizer-funded study demonstrated a difference by ethnicity in the mental health impacts of vitiligo (with vitiligo associated with a greater mental health burden in people of non-white ethnicity), the study was not designed to assess this as a primary outcome. Further analysis is required to fully understand these potential relationships as well as provide critical information on whether there is a socio-economic (SES) gradient in the mental health impacts of vitiligo. The previous study did not assess other potential disparities in management, such as healthcare utilisation of primary care encounters or dermatology services.

There is also substantial scope to expand on the previous study to provide, for the first time, a greater understanding of the total burden of vitiligo across the population, including reporting lifetime risk estimates for vitiligo, across sociodemographic groups. It is likely that substantial disease burden differences exist across these groups.

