5.7.2 Sociodemographic subgroups

Age, sex, deprivation and ethnicity will comprise the sociodemographic factors used for stratification of the outcome measures.

Age will be stratified into four age categories: 13-17 (adolescents), 18-20, 30-49, 50+.

Ethnicity will be grouped using the standardised definitions of major UK ethnic groups: White, Black, Asian, mixed, and others. (7)

Deprivation will be defined using the national deprivation measure; index of multiple deprivation (IMD) and stratified into quintiles of deprivation according to the national distribution. (8) IMD is calculated at the point of data extraction, using patient postcode (practice postcode where patient postcode is not available).

6. Sample Size Calculations

A sample size calculation is only applicable to the incidence of mental health conditions of anxiety and depression in people diagnosed with vitiligo.

Assuming 80% power, a 5% level of statistical significance and a background population prevalence of 15% for anxiety and 10% for depression,(9), our anticipated sample size for vitiligo (n = 8,000) will be sufficient to detect a risk difference of 1.11% in anxiety between those with and without vitiligo, and 1.12% difference in depression between those with and without vitiligo. Sample size calculations were performed in OpenEpi,(10) results are presented using methods of Kelsey.(11)

7. Populations to be Analysed

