7.3 Matching Process

For objectives 2-5, controls for each vitiligo case will be identified from the pool of people without a vitiligo diagnosis registered in the OPCRCD database at the time of vitiligo diagnosis for the case. Vitiligo cases will be eligible as controls up until the date of their vitiligo diagnosis (at which date their follow-up will be censored if selected as a control).

Each case will be assigned an index date at the time of their vitiligo diagnosis. Corresponding controls assigned to each case will have the same index date.

Each individual with vitiligo will be matched at their index date with up to four unaffected controls. Controls cannot be diagnosed with vitiligo at the date of matching and will require at least one year of follow-up time to minimise the risk of a non-recorded existing diagnosis of vitiligo. Time-updated exact matching will be performed by age, sex, ethnicity and deprivation, selected from the pool of eligible people registered in the same GP practice.

If required, a combination of time-dependent propensity score matching and exact matching will be performed to create a baseline matched dataset.

The matching process is subject to change depending on the feasibility of the mentioned matching process during the initial exploration of the data. The produced baseline matched dataset will be used for all analyses for objective 2-5.

8. Statistical Analysis

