8.1 Statistical Principles

Mean, standard deviation (sd) and any other statistical measures, will be reported to one decimal place. Continuous data will be summarised in the form of means, sd, median, interquartile range (IQR) and range as appropriate. Categorical data will be summarised using the frequencies and proportions. Chi-squared and t-tests will be performed to compare the frequency of dichotomous variables and the values of continuous variables where relevant. 95% CIs will be reported for main effect sizes. Statistical significance will be assessed using $p < 0.05$. Actual p-values will be reported except for p-values less than 3 decimal places which will be reported as “ < 0.001 ”. P-values > 0.1 will be reported to one decimal place, p-values between 0.01 and 0.1 will be reported to 2 decimal places, and p-values between 0.001 and 0.01 will be reported to three decimal places.

The assessment of any associations with baseline characteristics and the outcomes of interest (objectives 2-5) will be assessed using logistic regression (prevalent and incident outcomes), Cox proportional hazards (time to event outcomes) and Poisson regression (repeated event outcomes) models. Three different adjustment sets will be used for each endpoint analysis. These include: an unadjusted model, a sex and age adjusted model, and a multivariable model with an adjustment set of: age, sex, BMI, smoking status, alcohol use, and common comorbidities: type 2 diabetes, hypertension, atrial fibrillation, angina, acute myocardial infarction, stroke, heart failure, chronic liver disease, dementia, rheumatoid arthritis, asthma, chronic obstructive pulmonary disease, chronic kidney disease stages 3-5, malignancy and inflammatory bowel disease.

Assumptions of statistical approaches will be assessed, and transformations used if necessary.

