8.3 Secondary Endpoint Analysis

Objective 2

Anxiety and depression outcomes will be captured if occurring prior to, or within two years of, an individuals' study index date. Binary outcome logistic regression model outputs will be used to compare the burden of anxiety and depression in vitiligo cases compared to matched controls. Furthermore, additional analyses for new onset anxiety and depression outcomes will be conducted, excluding people with a previous record of the respective mental health condition. Anxiety and depression outcomes will be defined by the first occurrence of a relevant code in the primary care record up to two years post index-date. Cox proportional hazards regression will be used to estimate the excess risk of anxiety and depression outcomes in vitiligo cases versus controls. Results will be described as hazard ratios.

Objective 3

Parasuicide/suicide attempts will be defined by the first occurrence of a relevant code in the primary care record up to two years post index-date. People with a previous record of parasuicide/suicide attempt will be excluded from the calculations. Cox proportional hazards regression will be used to estimate the excess risk of parasuicide/suicide attempts in vitiligo cases versus matched controls. Results will be described as hazard ratios.

Adjustment disorder and sleep disturbance will be defined by the first occurrence of a relevant code in the primary care record up to two years post index-date. People with a previous record of the adjustment disorder will be excluded from the from the adjustment disorder endpoint analysis. Cox proportional hazards regression will be used to estimate the excess risk of the relevant condition in vitiligo cases versus matched controls. Results will be described as hazard ratios.

Objective 4

Dermatology referral and mental health referral or reviews will be defined by the first occurrence of a relevant code in the primary care record up to two years post index date. Cox proportional hazards regression will be used to estimate the excess risk of these outcomes in vitiligo cases versus matched controls.

For primary care encounters reviews, defined as a rate of encounters within two years after the index date, will be compared using generalised linear models with time-at-risk as an offset. Results will be described as incidence rate ratios.

Objective 5

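### Pre-index consultation frequency is neither matched on nor adjusted for, so the primary care visit-rate ratio has no baseline value and could exceed 1 without any vitiligo effect

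*Combined protocol and SAP*

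**What the plan says.** - **Matching (Section 7.3).** "Time-updated exact matching will be performed by age, sex, ethnicity and deprivation", from people registered at the same practice. Each case is "matched at their index date with up to four unaffected controls". Controls need a year of follow-up but need not have attended. A propensity score is held in reserve with no covariates named, and the matching may change after data exploration.
- **Adjustment (Section 8.1).** There are three sets: none; age and sex; and "a multivariable model with an adjustment set of: age, sex, BMI, smoking status, alcohol use, and common comorbidities", with 15 comorbidities listed. None contains a measure of earlier consultation.
- **Visit outcome (Section 8.3, Objective 4).** "For primary care encounters reviews, defined as a rate of encounters within two years after the index date, will be compared using generalised linear models". The offset is each person's time at risk. No pre-index rate enters.
- **Other outcomes (Section 8.3).** Mental health, referral and work outcomes are relevant codes in the primary care record within two years of index. The prevalent anxiety and depression analysis also counts codes made before index. The new-onset anxiety and depression, parasuicide and adjustment disorder analyses exclude people with an earlier record of that condition.
- **Attendance (Section 8.4).** A sensitivity analysis repeats the mental health, utilisation and work comparisons using only controls with an encounter in the year before index.
- **Limitations (Section 9).** Utilisation and work outcomes cannot all be tied to vitiligo, and causal interpretation is ruled out. Selection through attendance is not mentioned.

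**The concern.** A person becomes a case only when vitiligo is coded in the record, and a control need only be registered. Section 3.1 begins one sentence "Although vitiligo is typically asymptomatic", so some first codes may plausibly be made at visits for other reasons, which happen more often in people who attend often. Such cases would have had high visit rates anyway. The two-year visit-rate ratio, which Objective 4 reads as vitiligo-associated utilisation, would then be above 1 with no effect of vitiligo. Frequent attenders also have more occasions for a depression, sleep, referral or fitness-for-work code, so the hazard ratios that Section 8.3 presents as excess risk could be raised by the same route.

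Section 8.4 shows that the sponsor recognises bias from attendance. Its check drops controls with no prior-year visit, but a control with one visit and a case with twelve still count as comparable.

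**Working it through.** **What the documents supply.** They give no consultation rate, no spread of rates and no share of opportunistic first codes, so there is no plan figure on this point to reproduce. The only calculation in the plan is the sample size (Section 6), used below as a yardstick.

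**Assumed model, no true vitiligo effect.** Control visit rates are gamma with mean m = 5 a year and shape k = 1 or 2. A share f of first vitiligo codes arises in proportion to visit rate; the rest are unrelated to it. Prior-year and post-index counts are Poisson. There is no credit for matching or comorbidity adjustment.

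1. *Planned comparison.* A gamma sampled in proportion to its own value has mean m(1 + 1/k). The case mean is therefore m(1 + f/k), and the rate ratio is 1 + f/k.
2. *Section 8.4 restriction.* The share of controls with no prior-year visit is (k/(k+m))^k, and their mean rate is km/(k+m).
   - k = 1: share 1/6, mean 0.833. Remaining controls average (5 - 0.833/6)/(5/6) = 5.83.
   - k = 2: share 0.0816, mean 1.429. Remaining controls average (5 - 0.0816 × 1.429)/0.9184 = 5.32.
   - The ratio is 5(1 + f/k) divided by 5.83 or 5.32.
3. *Comparison within prior-year count.* A control with count n has expected rate (k+n)m/(k+m). Averaging over the cases' counts, whose mean is m(1 + f/k), gives a ratio of (1 + f/k)(k+m)/(k+m+mf/k).

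| f | k | Planned | Section 8.4 | Within prior count |
|---|---|---|---|---|
| 10% | 1 | 1.10 | 0.94 | 1.02 |
| 10% | 2 | 1.05 | 0.99 | 1.01 |
| 25% | 1 | 1.25 | 1.07 | 1.03 |
| 25% | 2 | 1.12 | 1.06 | 1.03 |
| 50% | 1 | 1.50 | 1.29 | 1.06 |
| 50% | 2 | 1.25 | 1.18 | 1.06 |

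A Poisson regression on simulated data with prior-count categories gave 1.02-1.07 for the last column, so the adjusted range is taken as 1.01-1.07. The Section 8.4 figure falls below 1 at small f because the rule removes low attenders from the controls only.

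**Less stable visit rates.** Let the pre- and post-index rates each equal the rate at coding with probability q = 0.5 or 0.7 (assumed), and otherwise be redrawn. The ratios become:
- planned: 1 + qf/k, or 1.03-1.35;
- Section 8.4: 5(1 + qf/k) divided by q² × (5.83 or 5.32) + (1 - q²) × 5, or 0.99-1.25;
- within prior count: (1 + qf/k)/(1 + q³mf/(k(k+m))), or 1.02-1.19.

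The largest adjusted values are at f = 50%, k = 1: 1.35/1.143 = 1.18 for q = 0.7 and 1.25/1.052 = 1.19 for q = 0.5. At f = 10-25%, adjustment leaves 1.02-1.10 and Section 8.4 leaves 0.99-1.09.

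**Rough scale for coded mental health outcomes.** Assume 20-30% of controls are frequent attenders, 1.1-2.0 times as likely to have vitiligo coded and with 1.5-3 times the outcome risk (v). With f0 and f1 the frequent-attender shares in controls and cases, the spurious ratio is (1 + f1(v-1))/(1 + f0(v-1)).
- Low end: f0 = 0.20, f1 = 0.22/1.02 = 0.216, v = 1.5, ratio 1.108/1.100 = 1.01.
- High end: f0 = 0.30, f1 = 0.60/1.30 = 0.462, v = 3, ratio 1.923/1.600 = 1.20.

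On the plan's 15% and 10% backgrounds, this is 0.1-3.0 points for anxiety and 0.1-2.0 for depression. Section 6 says that "our anticipated sample size for vitiligo (n = 8,000) will be sufficient to detect a risk difference of 1.11% in anxiety" and a "1.12% difference in depression between those with and without vitiligo". The spurious difference can fall on either side of those values. Those two figures did not reproduce: Kelsey, two-sided, at 1:4 gives 1.26 and 1.06 points. That is a separate matter, and nothing here depends on it.

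**The case against.** The strongest reply is that none of this has been observed. The documents say nothing about how often cases or controls attended, and the typically-asymptomatic remark is half a sentence. The rest of Section 3.1 stresses psychological impact and visibility, which are reasons to consult because of the vitiligo. The model also treats people as unmatched and unadjusted, whereas same-practice matching and 15 chronic conditions may absorb part of the difference in attendance. This stands: the ratios are illustrations, and probably high ones.

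The proposed adjustment is also imperfect. With unstable visit rates its advantage over the Section 8.4 check largely disappears at 10-25% opportunistic coding. That stands too, although only the adjustment addresses frequency among attenders, and only reported pre-index rates would show whether the imbalance exists.

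The plan is not silent either. Section 8.4 tests part of the problem and Section 9 disclaims causality for utilisation and work outcomes. But Section 9 does not mention selection through attendance, and its disclaimer does not extend to mental health outcomes.

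A reader might infer that this produces false sociodemographic disparities. The documents do not support that: a multiplicative bias of equal size in every subgroup cancels when subgroup ratios are compared, and nothing shows that it is unequal. It remains a possibility that the pre-index rates by subgroup would help to judge.

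**Conclusion.** The omission is certain: prior consultation frequency is absent from the matching and from all three adjustment sets, and the visit-rate ratio has no baseline value of its own outcome. The consequence is conditional. If coding of vitiligo rises with attendance, the visit ratio would be inflated, by about 1.05-1.50 under the stable-rate model and its assumed 10-50% share, before credit for matching and comorbidities. Section 8.4 can over- or under-correct.

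A reader might go further and conclude that the planned comparisons do measure frequent attendance, or that every Objective 2-5 result is biased by a known amount. The documents contain no data for either. Exposure also differs by outcome. Visits lack their own baseline. The analyses that exclude earlier records are less exposed. Prevalent anxiety and depression are exposed but cannot be repaired in this way, because that outcome counts codes made before index and the prior visits may follow from it. The change is worth making because it is cheap and makes any imbalance visible, not because bias has been shown.

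**What to change.** In Sections 8.1 and 8.3:

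- **Primary care visits.** Add the pre-index encounter rate to the multivariable model for cases and controls alike: encounters divided by registered time in a fixed window ending before the diagnostic work-up, for example months -18 to -6. Enter it in categories, with a separate category for little or no observed time. Present the baseline-adjusted rate ratio beside the planned estimates.
- **Description.** Report the pre-index rate by case/control group and by sociodemographic subgroup.
- **New-onset and first-event outcomes of Objectives 2-5.** Add the same covariate in a further adjusted or sensitivity model.
- **Prevalent anxiety and depression.** Do not use it there as a baseline adjustment.

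The cost is a short SAP addition and one variable derived from encounter data that Objective 4 and Section 8.4 already need. There are three drawbacks. Windows will be partial or empty for recent registrants: Section 7.2 excludes only cases diagnosed within 6 months of registration, so a case registered just over 6 months has almost no time in the example window. Visits for early vitiligo before month -6 would be adjusted away. Some residual bias would remain.

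### No adjustment set or matching factor includes mental health history before the index date, so the Objective 3-5 and new-onset Objective 2 ratios may mix prior illness with excess after diagnosis

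*Combined protocol and SAP*

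**What the plan says.** Section 8.1 of the combined protocol and SAP states that "Three different adjustment sets will be used for each endpoint analysis": unadjusted, age and sex, and "a multivariable model with an adjustment set of: age, sex, BMI, smoking status, alcohol use" together with "common comorbidities: type 2 diabetes, hypertension, atrial fibrillation, angina, acute myocardial infarction, stroke, heart failure, chronic liver disease, dementia" and six further conditions. Section 7.3 matches on age, sex, ethnicity and deprivation within practice. It allows a propensity score as a fallback but names no covariates for it.

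Section 3.1 reports that people with vitiligo carry more mental illness than people without it, and that "in people with vitiligo, mental health comorbidity is associated with higher levels of healthcare utilisation, time off work, and unemployment". It also reports an ethnic difference, "with vitiligo associated with a greater mental health burden in people of non-white ethnicity", and cautions that the earlier study did not have this as a primary outcome.

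Section 8.3 deals with history by exclusion. The new-onset anxiety and depression analyses are run "excluding people with a previous record of the respective mental health condition". Parasuicide/suicide attempt and adjustment disorder each exclude people with an earlier record of that same outcome.

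Section 9 says that disparities will be read on the assumption that the outcomes relate to vitiligo. It disclaims causal interpretation for healthcare use and work outcomes.

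**The concern.** A factor that the protocol's own background ties both to vitiligo and to an outcome is the usual candidate for adjustment. Here it is absent from the only model that adjusts for health history. Age and sex are already matched, so the second adjustment set adds little control.

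If cases enter follow-up with more past depression or anxiety than controls, part of the excess in mental health referrals, GP encounters, sick notes or unemployment may be illness that was there at the index date. Objectives 2-5 ask about disparities. If the case-control gap in prior illness differs by ethnicity, the size of this mixing differs too, and a comparison of ratios between ethnic groups becomes harder to read.

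**Working it through.** **Step 1: count the terms.** The plan lists "common comorbidities: type 2 diabetes, hypertension, atrial fibrillation, angina, acute myocardial infarction, stroke, heart failure, chronic liver disease, dementia, rheumatoid arthritis, asthma" (11 conditions), then "chronic obstructive pulmonary disease, chronic kidney disease stages 3-5, malignancy and inflammatory bowel disease" (4 conditions): 11 + 4 = 15. Dementia is the nearest to a mental health term. Terms for prior depression, anxiety or other mental health history number 0 in the adjustment sets and 0 in the matching.

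**Step 2: see what the exclusions cover (Section 8.3).**

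| Endpoint | Prior record of the same outcome excluded? | Other mental health history handled? |
|---|---|---|
| New-onset anxiety, new-onset depression (Obj. 2) | Yes | No |
| Parasuicide/suicide attempt (Obj. 3) | Yes | No |
| Adjustment disorder (Obj. 3) | Yes | No |
| Sleep disturbance (Obj. 3) | None stated | No |
| Mental health referral or review (Obj. 4) | None stated | No |
| Primary care encounters (Obj. 4) | None stated | No |
| Unemployment, time off work (Obj. 5) | None stated | No |

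A person with earlier depression therefore stays, unadjusted, in the new-onset anxiety, parasuicide and adjustment disorder models. A person already under mental health review before the index date can count as an event after it.

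**Step 3: illustrate the size.** The plan gives no figure to reproduce. For an omitted yes/no factor with prevalence p1 in cases and p0 in controls, which multiplies the outcome rate by R, and with no true vitiligo effect:

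bias factor = (1 + p1(R − 1)) / (1 + p0(R − 1))

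For hazard ratios this is an approximation. Inputs:
- p0 = 10% or 15%, the background prevalences in Section 6. They are a proxy only: the title of the source cited there refers to 12-month disorders, not to history ever recorded.
- Excess in cases = 1.11, 3 or 5 percentage points (assumed). The lowest borrows a detectable difference from Section 6, which is not a stated gap in history.
- R = 1.5 to 5 (assumed).

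| p0 | p1 | R = 1.5 | R = 2 | R = 3 | R = 5 |
|---|---|---|---|---|---|
| 10% | 11.11% | 1.005 | 1.010 | 1.018 | 1.032 |
| 10% | 13% | 1.014 | 1.027 | 1.050 | 1.086 |
| 10% | 15% | 1.024 | 1.045 | 1.083 | 1.143 |
| 15% | 16.11% | 1.005 | 1.010 | 1.017 | 1.028 |
| 15% | 18% | 1.014 | 1.026 | 1.046 | 1.075 |
| 15% | 20% | 1.023 | 1.043 | 1.077 | 1.125 |

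For example, 15% v 20% with R = 3 gives 1.40/1.30 = 1.077. The range is about 1.005 to 1.14. A higher prevalence with the same excess stays inside it: 25% v 30% with R = 5 gives 2.20/2.00 = 1.10.

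**Step 4: illustrate the ethnicity comparison.** Assume 15% history in controls of both groups, 16% in white cases and 20% in non-white cases. The ratio of the two bias factors is (1 + 0.20(R − 1)) / (1 + 0.16(R − 1)):
- R = 1.5: 1.10/1.08 = 1.019
- R = 3: 1.40/1.32 = 1.061
- R = 5: 1.80/1.64 = 1.098

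The 16% v 20% split is invented for illustration; the documents give no such figures.

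**The case against.** The strongest reply is that prior mental illness may be a consequence of vitiligo rather than a confounder. The index date is the first coded diagnosis, not disease onset. Section 3.1 suggests that visibility, uncertain prognosis and lack of cure could explain the burden, and the Objective 2 burden analysis deliberately counts illness recorded before the index date. On that view adjustment removes part of what the study wants to describe. This stands. It is why the existing multivariable model should not be altered: the two simpler sets lack BMI, smoking, alcohol and every comorbidity, so no well-adjusted total association would be left.

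Three stronger readings are tempting, and the documents do not support them:
- A reader might infer that the protocol says prior mental illness drives the Objective 3-5 outcomes. Section 3.1 reports an association, within people with vitiligo, with healthcare use and work outcomes only. It does not mention the Objective 3 outcomes and does not specify illness before the index date.
- A reader might infer that the plan ignores history throughout Objective 3. Two of its three outcomes exclude a prior record of the same outcome.
- A reader might infer that a false ethnic disparity will result. If the extra burden flows from vitiligo, a larger ratio in non-white people is the disparity that the study sets out to describe.

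It is also fair to say that Section 9 already disclaims causal reading. That disclaimer covers healthcare use and work outcomes, not Objective 3 or new-onset anxiety and depression, and Section 8.3 still presents the Cox results as excess risk in cases.

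**Conclusion.** The gap is real and rests on the text alone: nothing in the stated matching or adjustment covers pre-index mental health history, and the exclusions cover only the same condition for some endpoints. The background supports the concern directly for Objectives 4 and 5. For Objective 3, and for the other condition in the new-onset anxiety and depression models, it is a reasonable inference.

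The size cannot be determined from the documents. The range of about 1.005 to 1.14 depends wholly on an assumed excess of 1.11 to 5 points and an assumed rate multiplier of 1.5 to 5. At the low end it is negligible; at the high end it could matter for a modest hazard ratio or a comparison between subgroups. Whether prior history is a confounder, an early effect of vitiligo or both cannot be settled here. The case is therefore for showing results with and without it: a cheap improvement, not the correction of an invalid model.

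**What to change.** Keep the three adjustment sets in Section 8.1 and make these changes:
- Add a fourth set for Objectives 3-5: the multivariable set plus depression and anxiety ever recorded before the index date, each yes/no.
- In the new-onset Cox models, add the other condition's history: prior depression in the anxiety model and prior anxiety in the depression model.
- Leave the Objective 2 burden logistic model unchanged, because prior history is part of that outcome.
- Fit the fourth set for parasuicide/suicide attempt and adjustment disorder only where event numbers allow; Section 9 already expects few events.
- Report the third and fourth sets side by side, overall and by sociodemographic subgroup. State that the fourth may remove illness caused by vitiligo before it was coded, so it shows the association beyond prior mental health history, not the total association.

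The cost is a short SAP amendment and one further model per endpoint. Depression and anxiety before the index date are already captured for Objective 2, so no new extraction should be needed.
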